All procedures will be conducted by UNC investigators, including board-certified otologists and an audiologist. Fully informed consent will be obtained from all subjects.

A. Participants

Subjects must meet the following inclusion criteria and not exhibit any of the exclusion criteria.

- 1. Inclusion Criteria
 - a. Scheduled to undergo a surgical procedure that will result in profound hearing loss in the surgical ear
 - i. Unilateral, vestibular schwannoma with planned translabyrinthine surgery or unilateral Meniere's disease with planned labyrinthectomy
 - ii. Diagnosed by UNC investigators
 - b. $PTA \le 35 \text{ dB HL}$ in the contralateral ear
 - i. No evidence of retrocochlear dysfunction
 - c. Unaided CNC word score $\ge 80\%$ in the contralateral ear
 - d. Greater than 18 years of age at implantation
 - e. Realistic expectations
 - f. Willing to obtain appropriate meningitis vaccinations
 - g. No reported cognitive issues
 - i. Pass the Mini Mental State Examination (MMSE) screener
 - h. Able and willing to comply with study requirements, including travel to investigational site
 - i. Obtain CDC recommended meningitis vaccinations prior to surgery
- 2. Exclusion Criteria
 - a. History of implantable technology in either ear, such as a boneconduction implant
 - b. Non-native English speaker
 - i. Speech perception materials are presented in English
 - c. Inability to participate in follow-up procedures (i.e., unwillingness, geographic location)
- 3. Enrollment
 - a. This study seeks to enroll ten (10) subjects.
- B. Timeline

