 - i. Medical Evaluation
 - a. This is standard of care.
 - b. Subject will be seen by the physician
 - ii. Audiologic Evaluation
 - a. Unaided air and bone conduction thresholds
 - i. Air-conduction assessed with insert phones
 - b. Initial Activation of External Speech Processor (approximately 2-4 weeks postoperatively)
 - i. Unaided air and bone conduction thresholds
 - a. Air-conduction assessed with insert phones
 - ii. Unaided word recognition with CNC words in both ears
 - a. Unaided word recognition testing is conducted in quiet in the effected ear
 - b. Masking will be presented to the contralateral ear if indicated
 - iii. Initial activation of external speech processor
 - a. Subjects will be fit with the commercially available MED-EL SONNET external speech processor (MED-EL Corporation, Innsbruck, Austria). Speech perception and localization measures will be conducted with the subject listening with the SONNET external speech processor for the aided conditions.
 - iv. Counseling on the external device and use
 - c. 1-month Post-Initial Activation
 - i. Completion of test battery listed in VI.C.
 - d. 3-months Post-Initial Activation
 - i. Completion of test battery listed in VI.C.
 - e. 6-months Post-Initial Activation
 - i. Completion of test battery listed in VI.C.
 - f. 9-months Post-Initial Activation
 - i. Completion of test battery listed in VI.C.

- g. 12-months Post-Initial Activation (study endpoint)
 - i. Completion of test battery listed in VI.C
- C. Test Battery

The following test battery will be completed at each post-initial activation interval (1, 3, 6, 9 and 12 months). All assessment and mapping will be conducted at the Carolina Crossing research lab by a board-certified audiologist.

- 1. Unaided Diagnostic Assessment
 - a. Air- and bone-conduction thresholds in both earsi. Air-conduction assessed with insert phones
 - b. Unaided word recognition with CNC words in both ears
 - a. Unaided word recognition testing is conducted in quiet in the effected ear
 - b. Masking will be presented to the contralateral ear if indicated
- 2. Tympanometry for each ear
- 3. Sound Field Measures

The Carolina Crossing research lab features a 180° arc with 11 speakers spaced 18° apart. This arc will be utilized during the speech perception and localization measures.

- a. Aided thresholds with the external speech processor on and masking applied to the contralateral ear will be measured using pulsed, warble tones

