 - 1. Demonstrate an improvement in speech perception abilities in an aided (cochlear implant on) versus an unaided (cochlear implant off) condition
 - 2. Demonstrate an improvement in localization abilities in an aided (cochlear implant on) versus an unaided (cochlear implant off) condition
 - 3. Demonstrate an improvement in subjective report in an aided (cochlear implant on) versus an unaided (cochlear implant off) condition

VIII. Statistical Analysis

- A. Descriptive summaries will be provided for the following: subject demographics, and frequency of major and minor complications/adverse events.
- B. A single-subject design will be utilized, where each subject serves as his or her own control, for analysis of objective and subjective results. A singlesubject design was chosen in order to accommodate the heterogeneity that is well known to characterize auditory prosthesis research. Repeated-measures ANOVA will be calculated with a p-value of ≤ 0.05 for statistical significance. Statistical analysis will be conducted with SPSS software.
 - 1. Comparison in aided speech perception performance on word and sentence materials in the post-initial activation intervals
 - a. Also compare the difference between the aided and unaided conditions at each follow-up interval
 - 2. Comparison in localization abilities in the post-initial activation intervals
 - a. Also compare the difference between the aided and unaided conditions for each follow-up interval
 - 3. Comparison in subjective report in the post-initial activation intervals

If needed, statistical consultation will be sought from the North Carolina Translational and Clinical Sciences Institute (TraCS) or UNC Odum Institute.

IX. Endpoints

- A. Safety endpoint
 - 1. The primary safety endpoint is the evaluation of Adverse Events. All Adverse Events will be reported to the UNC IRB. If the UNC IRB or study investigators deem an Adverse Event unacceptable, then this would be sufficient terms to terminate the study.
- B. Primary effectiveness endpoint

1. The primary effectiveness endpoint is the comparison of speech perception (VII.A.1), localization abilities (VII.A.2) and/or subjective report (VII.A.3) when the cochlear implant is on versus off.

X. Risk Analysis

A. Potential risks

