- A. Subjects will be monitored on a case-by-case basis for ongoing or unanticipated medical complications. Adverse events will be tracked on a case-by-case basis and recorded in study binders at the time of occurrence and followed up at resolution. Any adverse event will be reported to the UNC IRB. Should there be concern for the safety of subjects because of their participation in the study by the investigators or the UNC IRB, the study would be halted at least temporarily and a detailed discussion with the investigators and UNC IRB would be undertaken to evaluate the viability of the study.
- B. Subjects can withdraw from the study at any time by notifying the Primary Investigator. If the investigator identifies the need to withdraw a subject from the study for any reason, this will be discussed in person during a scheduled evaluation. In either scenario, the subject will continue to receive care irrespective of their participation in the study. Should a subject not be able to receive auditory stimulation from the cochlear implant, or develops a complication related to participation in the study, their participation in the study will end when their study related morbidity has resolved or is no longer active. Again, this will not affect the medical care for the subject.

XIV. Confidentiality

A. Subjects will be assigned a specific, anonymous subject number that will be associated with his or her data. Database entry will be by subject number

only. All personal identifiers will be kept in a separate, secure data file that will be password protected and not associated with the study data. Only investigators will have access to the subject numbers.

- B. Subject specific binders will be maintained in a locked cabinet in the Carolina Crossing research lab. Individual data collection sheets will be coded with the subject number and placed in the subject specific binder at each interval. For analysis, the data will not included identifiable information.
- C. Data will not be shared outside the investigative team except during reporting of anonymous results.
- D. After the closure of the study, subject data will be retained for seven years. At that time, paper data will be shredded and destroyed in a HIPAA compliant manner. Electronic data will be destroyed following UNC policy.
- E. A description of the clinical trial will be available on http://ClinicalTrials.gov. This web site will not include information that can identify research subjects.

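### The across-interval repeated-measures ANOVA, as ordinarily run in SPSS, drops any subject with one missed visit; a mixed model on all attended visits would keep them

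*Combined protocol and SAP*

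**What the plan says.** Section VI.A.3 sets the size: "This study seeks to enroll ten (10) subjects". Section VI.C fixes five repeated assessments: "The following test battery will be completed at each post-initial activation interval (1, 3, 6, 9 and 12 months"). The whole battery belongs to each visit, so a missed visit loses every outcome for that visit.

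Section VIII.B names the method and the software: "Repeated-measures ANOVA will be calculated with a p-value of ≤ 0.05 for statistical significance. Statistical analysis will be conducted with SPSS software". It does not name the SPSS procedure. Two kinds of comparison are listed under it:

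- Across visits. For speech: "Comparison in aided speech perception performance on word and sentence materials in the post-initial activation intervals". Localization and subjective report are worded in the same way.
- Within a visit. For speech: "Also compare the difference between the aided and unaided conditions at each follow-up interval". Localization has a matching item. Subjective report does not, so its only listed analysis is across visits.

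Section XIII.B says: "Subjects can withdraw from the study at any time by notifying the Primary Investigator". It also ends participation, once any study-related morbidity has settled, for a subject who gets no auditory stimulation or has a study-related complication. Section VI.A requires subjects to be able and willing to comply and to travel, and excludes those who cannot take part in follow-up. The documents state no missing-data rule, visit window, replacement rule, dropout allowance or expected missed-visit rate.

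**The concern.** Classical repeated-measures ANOVA over five visits needs a value in all five cells for each subject. A subject who misses the 6-month visit, or leaves after 9 months, contributes nothing to the visit comparison, although three or four attended visits of data are on file. With ten subjects, each such loss is a tenth of the sample. Because the battery is given as a block, the same subject disappears from the speech, localization and questionnaire analyses together. This is separate from the score-gated HINT and AzBio steps, which can leave further empty cells even with full attendance.

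At stake are the precision and power of the across-interval comparisons, and whether they describe all implanted subjects or only those with perfect attendance.

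**Working it through.** The documents contain no power, effect size, SD or dropout figure, so there is no figure of the plan's own to reproduce.

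**Inputs from the documents.** n = 10 (VI.A.3); 5 visits (VI.C); repeated-measures ANOVA at 0.05 (VIII.B).

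**Assumed input.** A per-visit missed rate m of 1% to 10%, independent across visits and subjects.

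**Step 1: subjects lost.** A subject is complete with probability (1 − m)^5, so the expected loss is 10 × [1 − (1 − m)^5]. If only one visit is needed, the expected loss is 10 × m.

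| m (assumed) | Expected loss, all five visits required | P(at least 1 lost) | P(at least 2 lost) | Expected loss, one visit required |
|---|---|---|---|---|
| 1% | 0.5 | 40% | 8% | 0.1 |
| 2% | 1.0 | 64% | 25% | 0.2 |
| 3% | 1.4 | 78% | 42% | 0.3 |
| 5% | 2.3 | 92% | 70% | 0.5 |
| 10% | 4.1 | >99% | 96% | 1.0 |

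For example, at 5%: 0.95^5 = 0.774, and 10 × (1 − 0.774) = 2.3. An expected loss of two needs m = 1 − 0.8^(1/5) = 4.4%; a loss of four needs m = 1 − 0.6^(1/5) = 9.7%.

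Independence is the unfavourable case. At 5%, 50 × 0.05 = 2.5 of the 50 subject-visits are missed on average. If they all fall in one subject, one subject is lost, not 2.3.

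**Step 2: data discarded.** Attended subject-visits are 50(1 − m); those kept by complete cases are 50(1 − m)^5. The share of collected data discarded is 1 − (1 − m)^4.

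- 5%: 47.5 attended, 38.7 kept, 19% discarded.
- 10%: 45 attended, 29.5 kept, 34% discarded.

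**Step 3: power for the visit effect.** The simulation used 10 subjects, visit means 0, 0.75, 1.2, 1.43 and 1.5, subject SD 1.5, residual SD 1 and independent missingness. All these values are assumed. It compared the complete-case F test with the same within-subject F test on all attended visits. The second test stands in for the mixed model and is not a REML fit. Full-data power is about 85%.

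| m (assumed) | Complete-case | All attended visits |
|---|---|---|
| 5% | about 71% | about 82% |
| 10% | about 52% | about 78% |

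At 1%, 2% and 3% missed, complete-case power is about 82%, 79% and 77%. With the visit means multiplied by 1.5, it is about 96% at 5% missed and 87% at 10%. With the means doubled, it stays above 95% at both rates.

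**Step 4: a check on the remedy.** Suppose on and off are put in one model across visits with only a subject random intercept. The on/off effect is then tested against pooled residual error. Simulating no true on/off effect (10 subjects, 5 visits), the nominal 5% error rate became about 8%, 15% and 32% when the subject-by-condition SD was 0.25, 0.5 and 1.0 of the residual SD. Testing each subject's mean on-minus-off difference stayed near 5%.

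**The case against.** The strongest reply is that the main contrast is largely untouched. Section IX.B makes implant on versus off the primary effectiveness comparison, and VIII.B plans it interval by interval for speech and localization. Both conditions are tested in the same visit, so run that way the contrast loses only those absent that day: 0.5 subjects at 5%, 1.0 at 10%. This stands. It does not cover the across-interval comparisons. Nor does the plan rule out a single condition-by-visit ANOVA, which would have the full problem.

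Second, the missed-visit rate and the growth curve are assumed, entry criteria favour attenders, and larger effects lose less power. This stands too, and is why ranges are given. Even so, at 2% missed the chance of losing at least one subject is 64% under independence.

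Third, SPSS also has a procedure that does not delete such subjects, the plan does not say which it will use, and VIII.B allows for statistical consultation. That is true, so the deletion is inferred. But the wording ordinarily means the complete-case procedure, and no rule says otherwise.

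A reader might go further and infer three things that the documents do not support:

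- That two to four subjects will be lost from every outcome. This needs a missed rate of about 4–10% that the documents do not give, and it overlooks the per-interval on/off comparisons.
- That most of the data are wasted. The share is 19% at 5% missed and 34% at 10%.
- That the remaining subjects will be those doing best. Section XIII.B provides an outcome-related exit for subjects with no stimulation, so selection is possible. The simulation used independent missingness and shows no such bias.

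**Conclusion.** The point holds for the across-interval comparisons of aided speech perception, localization and subjective report. The named method, as ordinarily run, discards attended visits that a method in the same software would use. Subjective report is the most exposed, because no within-visit analysis is listed for it.

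The size depends on an unstated missed rate. It is modest at 1–3% per visit, about one subject or fewer on average up to 2% and 1.4 at 3%. It is material at 5–10%, with about 11 points of power lost to deletion at 5% (82% − 71%) and 26 at 10% (78% − 52%). Those power figures belong to one assumed curve and to independent misses. The on/off contrast for speech and localization is affected only if it is fitted across all five visits at once. The plan should be changed, but this point does not undermine the primary comparison when that is run visit by visit.

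**What to change.** In VIII.B, for the across-interval comparisons, replace repeated-measures ANOVA with a linear mixed model fitted by REML in SPSS MIXED to all attended visits. Use visit as a fixed effect, subject as a random effect, and Satterthwaite or Kenward-Roger degrees of freedom. State that no attended visit is excluded because another was missed. Show the complete-case ANOVA as a sensitivity analysis.

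For on versus off, state one of two approaches:

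- compare the paired on-minus-off differences at each visit, in all subjects seen at that visit; or
- if on and off are modelled jointly across visits, include a random subject-by-condition term, so that the contrast is not tested against pooled residual error. Small-sample degrees of freedom do not make up for leaving this term out.

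The cost is SAP wording: the software is the same and no new data are needed. There are two drawbacks. The mixed model relies on data being missing at random, which is a weaker assumption than complete-case analysis needs but does not cure outcome-related withdrawal; reasons for missed visits and withdrawals should therefore be reported. The extra variance term may also be hard to estimate with ten subjects, which favours the per-visit paired comparison if the joint model does not fit.

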 - i. Frequencies assessed: 250-8000 Hz, including all inter-octaves
- b. Speech Perception Measures
 Speech perception will be assessed in an aided (cochlear implant speech processor on) and unaided (cochlear implant speech processor off) condition.
 Recorded materials will be presented at 60 dB SPL.
 - i. Speech Perception in Quiet
 - a. Listening condition
 - i. Speech 0° azimuth
 - b. Speech perception materials
 - i. CNC words
 - ii. CID sentences
 - iii. HINT sentences (if >50% correct on CID sentences)
 - iv. AzBio sentences (if >50% correct on HINT sentences)

- ii. Speech Perception in Noise
 - a. Listening conditions
 - i. Speech and noise 0° azimuth
 - ii. Speech 0° azimuth and noise to implanted side
 - iii. Speech 0° azimuth and noise to contralateral ear
 - b. Speech perception materials
 - i. HINT sentences
 - a. If >50% at SNR+10, then SNR+5
 - b. If >50% at SNR+5, then SNR+0
 - ii. AzBio sentences
 - a. If >50% at SNR+10, then SNR+5
 - b. If >50% at SNR+5, then SNR+0
 - iii. BKB-SIN sentences with adaptive SNR
- iii. Listening Conditions
 - a. Cochlear implant only (contralateral ear masked)
 - b. Contralateral ear only (cochlear implant speech processor off)
 - c. Combined (Cochlear implant on + contralateral ear unmasked)
- c. Localization

Localization will be assessed in an aided (cochlear implant speech processor on) and unaided (cochlear implant speech processor off) condition.

- i. The stimulus is a 200-ms speech-shaped noise, presented at 70dB-SPL from one of the 11 speakers (evenly spaced -180 to 180 degrees), selected at random.
- ii. The listener will be facing the center speaker during stimulus presentation. The task is to identify the source of the noise via a touchscreen monitor. No feedback is provided.
- iii. Data will be analyzed in terms of error and adjusted constant error, as described by Grantham et al (2007).
- iv. Listening Conditions
 - a. Contralateral ear only (cochlear implant speech processor off)
 - b. Combined (Cochlear implant on + contralateral ear unmasked)
- 4. Subjective questionnaires
 - a. Speech, Spatial and Qualities of Hearing Scale (SSQ) Gatehouse & Noble (2004)
 - b. Abbreviated Profile of Hearing Aid Benefit (APHAB) Cox & Alexander (1995)

VII. Proposed Claims

- A. Demonstrate the safety and effectiveness of cochlear implantation in populations suffering from unilateral profound hearing loss after labyrinthectomy or translabyrinthine surgical approaches.

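### The interval test on aided speech scores (VIII.B.1) cannot separate growing implant benefit from test practice, and no test is stated of whether the on-off difference changes over time

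*Combined protocol and SAP*

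**What the plan says.** Section VIII.B makes each subject his or her own control and applies a repeated-measures ANOVA at p ≤ 0.05. Its items on speech and localization are:

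- VIII.B.1, speech over time: "Comparison in aided speech perception performance on word and sentence materials in the post-initial activation intervals".
- VIII.B.1.a, speech on versus off: "Also compare the difference between the aided and unaided conditions at each follow-up interval".
- VIII.B.2, localization over time: "Comparison in localization abilities in the post-initial activation intervals". No listening condition is named. B.2.a adds an on-off comparison for each interval.

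The data come from Section VI.C: "The following test battery will be completed at each post-initial activation interval (1, 3, 6, 9 and 12 months"). For speech, "Speech perception will be assessed in an aided (cochlear implant speech processor on) and unaided (cochlear implant speech processor off) condition". Speech is heard three ways: implant only with the other ear masked, "Contralateral ear only (cochlear implant speech processor off"), and Combined. Localization uses the last two.

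The effectiveness claims concern on versus off, not change over time. For speech, VII.A.1 reads "Demonstrate an improvement in speech perception abilities in an aided (cochlear implant on) versus an unaided (cochlear implant off) condition". The primary effectiveness endpoint (IX.B.1) compares speech perception, localization "and/or subjective report (VII.A.3) when the cochlear implant is on versus off".

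The plan does not mention practice, list rotation, test order or a familiarisation session. Appendix B shows no sound-field speech or localization testing before month 1.

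**The concern.** The same listeners meet the same kinds of material five times with no run-in, so any learning of the tests falls inside the analysed window. VIII.B.1 uses processor-on scores only. A significant interval effect there has at least two explanations, adaptation to the implant and practice on the tests, and the analysis has no control condition to choose between them.

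That control exists in the data, because off scores are taken at every visit. If practice raises on and off scores alike, it drops out of their difference, and a change in that difference over time would point to the implant. VIII.B.1.a and B.2.a stop short of this: read naturally, they are separate contrasts at each visit. At stake is what the report can say about the time course. A statement that implant benefit grows between 1 and 12 months would lack a test that supports it.

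**Working it through.** The plan gives no power, effect size, SD or practice effect, so there is no figure of its own to reproduce. The check below shows how the two interval tests behave under stated assumptions.

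**Inputs from the documents.** n = 10 (VI.A.3), k = 5 visits (VI.C), repeated-measures ANOVA at 0.05 (VIII.B).

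**Assumed inputs.** Within-visit SD σ of 5, 8 or 12 points, with errors independent between visits and between conditions. Total practice gain P of 3, 5 or 10 points, reached as 0, 40, 70, 90 and 100% over the five visits. Sphericity. No implant-related change unless stated.

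**Aided-only test.** The F test has k − 1 = 4 and (k − 1)(n − 1) = 36 degrees of freedom, with critical value 2.634. The practice profile has mean 0.6 and deviations −0.6, −0.2, 0.1, 0.3 and 0.4. Their squares sum to 0.36 + 0.04 + 0.01 + 0.09 + 0.16 = 0.66. The noncentrality is

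λ = n × 0.66 × P² / σ² = 6.6 P² / σ².

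For P = 5 and σ = 5, λ = 6.6 × 25 / 25 = 6.6, and the chance of a significant result is 46%. All settings:

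| Total practice | SD 5 | SD 8 | SD 12 |
|---|---|---|---|
| 0 points | 5% | 5% | 5% |
| 3 points | 18% | 9% | 7% |
| 5 points | 46% | 19% | 11% |
| 10 points | 98% | 67% | 32% |

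Simulation with 20,000 trials per setting agrees to within about 1 percentage point.

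A steeper assumption, practice rising by a constant s points per visit with no plateau, gives λ = 10 × 10 s² / σ². At SD 8 and SD 6 the rates are 13% and 20% for s = 1, 43% and 70% for s = 2, and 81% and 98% for s = 3. The last case means 12 points gained by the fifth visit.

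**Condition-by-interval test.** This is the same F test on the on-minus-off difference, whose error variance is 2σ². If off scores show a share q of the practice, the difference keeps (1 − q)P, so

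λ = 6.6 (1 − q)² P² / (2σ²).

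Over P = 3 to 10 and σ = 5 to 12:

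- q = 1: λ = 0, so 5% in every setting.
- q = 0.5: 5% to 24%.
- q = 0: 6% to 79%.

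**Within-visit on-versus-off contrast at 12 months.** In the simulation the paired t-test stays at about 5% in every setting with q = 1. With q = 0.5 it runs from 5% to 51%.

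**Power cost.** Take a true 10-point gain in on scores only, with the same profile and no practice. The aided-only λ is 660 / σ² and the interaction λ is 330 / σ².

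| SD | Aided-only | Condition by interval |
|---|---|---|
| 5 | 98% | 79% |
| 8 | 67% | 36% |
| 12 | 32% | 17% |

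**The case against.** The strongest reply is that the plan makes no claim about growth. VII.A and IX.B.1 are framed as on versus off, and shared practice already cancels in that contrast within a single visit. This stands. A reader might infer that the plan counts practice as implant gain, or that the primary comparison is contaminated. The documents support neither: no text gives the aided trend that meaning, and the primary contrast is untouched by practice that both conditions share equally.

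A reader might also infer that localization is analysed on aided scores alone. VIII.B.2 does not say so; it leaves the condition open. The localization task also uses a randomly chosen speaker and gives no feedback, which should limit learning.

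It can be said that VIII.B.1.a, under a repeated-measures ANOVA, does not exclude an interaction. That is true, but it does not state one either.

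Finally, the off scores are an imperfect control. Contralateral-only is the match for Combined, and implant-only scores have no matched off score. Entry requires an unaided CNC score of at least 80% in the contralateral ear (VI.A.1.c), so off scores in quiet may sit near ceiling and show less practice. This also stands. It limits the remedy to the matched pair, makes it most useful in noise and localization, and argues against dropping the aided trends.

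**Conclusion.** The point holds in a limited form. The VIII.B.1 test cannot by itself distinguish growing implant benefit from practice. VIII.B.2 does not identify its condition, and the plan states no test of whether the on-off difference changes over time. The gap concerns the time-course analysis, not the primary on-versus-off contrast.

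The size depends wholly on assumptions, since the documents give neither a practice effect nor an SD. With a plateauing practice gain of 3 to 5 points in total, the aided-only test is significant in 7% to 46% of trials with no implant-related change. The 98% figures need 10 to 12 points of practice and a small SD. The 5% rate for the interaction rests on equal practice in both conditions. This is a cheap improvement to what the interval analysis can conclude, not a defect that undermines the trial.

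**What to change.** In VIII.B.1 and B.2, fit the repeated-measures ANOVA with condition (Combined versus contralateral-only) and interval as within-subject factors, for speech (chiefly the noise measures) and for localization. State that any claim of implant benefit growing over time rests on the condition-by-interval term. Name the listening condition in VIII.B.2.

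Keep the aided and implant-only trends, but describe them as change in performance that may include practice, not as evidence of growing implant benefit.

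The change is to SAP wording; the scores are already collected at every visit. It has two costs. The interaction has clearly less power than the aided-only test, as the last table shows, and with 10 subjects a null interaction should not be read as absence of growth. Cancellation is also only partial where off scores in quiet are near ceiling, so results in quiet should carry that caveat.
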